Each individual enrolled will participate in the study for approximately 3 months. We anticipate enrollment of study subjects will take approximately 15 months. We hope to complete all analyses 2 two years.

STUDY ENDPOINTS:

The primary study endpoints are we have enough patients enrolled to compare VAD-care SBML training and usual training groups.

PROCEDURES INVOLVED:

Approximately 60 advanced HF patients undergo VAD implantation at NMH yearly. During our 15-month study period, up to 75 participating patients and 75 caregivers will be eligible to receive either the SBML VAD self-management curriculum or usual VAD training. Eligible patients will be about to undergo VAD implantation at NMH, age >18, and English-speaking. Eligible caregivers will be identified by a VAD implantation patient, age >18, and English-speaking. Advanced HF patients who are scheduled for VAD implantation will receive information about the study at their pre-implantation clinic visits or during hospitalization. Consenting patients will be asked to provide the name and contact information of their primary caregiver; we will contact the caregivers to explain the study and assess their interest. Patients and caregivers must both agree to participate in the study to be enrolled. All Patient and caregiver VAD self-management training begins before implantation and continues up to the hospitalization for VAD placement.

Study randomization will be conducted via random number generator. After randomization, demographic data including age, sex, race/ethnicity, and socioeconomic (SES) factors such as zip code, highest level of education, and employment status will be collected from patients and caregivers.

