Two VAD nurses will perform usual training only, which is the current standard of care. First, patients and caregivers watch a video produced by the VAD manufacturer. Subsequently, the VAD nurse trains the patient and caregiver per usual routine with a non-implanted VAD. These meetings occur 1 to 3 times depending upon patient and caregiver availability and are not standardized. During the VAD implantation hospitalization, the caregiver completes a written examination to assess knowledge. The VAD nurse observes patient and caregiver completion of skills and deems competence based only on observation. Historically, patient and caregivers are variably able to participate in training sessions. If the patient is too ill to participate in training before VAD implantation, only the caregiver completes training and the patient is trained during the hospital stay for implantation at which point they are significantly clinically improved.

Three VAD nurses will administer SBML training. The SBML training group will first 1) watch the VAD video, then 2) participate in pre-intervention assessments using the simulator for a) driveline exit site sterile dressing changes; b) performing controller self-tests; c) changing power sources; d) troubleshooting emergent VAD-related malfunction; and e) recognizing specific signs and symptoms requiring immediate contact with the VAD team. The patient and caregiver

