We will estimate checklist score inter-rater reliability using the Kappa (κ) coefficient^{84,87}. Our prior work shows the difference between traditional training and SBML interventions is approximately 33%; traditionally trained simulated skill checklist performance averages 61.47% (SD=24.48) items correct while SBML training performance averages 94.88% (SD=6.63).^{9,48,51,53,88} We anticipate the usual training group in our study will perform similarly to the traditionally trained healthcare providers in our prior studies. Sample sizes of 65 in each group (total =130) achieve 82% power to detect at least 10% difference between the usual group and the SBML training group assuming a mean checklist score of 85% in usual group (SD=25) and 95% in the SBML training group (SD=10) with a significance level of 0.05 using a two-sided t-test. As the distribution of % items correct is likely to be non-parametric, adding 15% requires 75 in each group.⁸⁹ Therefore, our study will be overpowered to detect a 33% difference. We will compare checklist scores on actual patient assessments between usual care and SBML-trained groups using the independent t-test or Wilcoxon rank sum test (if data are non-parametric). We will compare age, sex, race/ethnicity, level of education, employment status, zip code, type of VAD, and VAD indication (DT vs. BTT) between groups using either Chi Square test or independent t-tests. If there is a difference between the randomized groups in any of these variables at the level of $p \leq 0.1$, we will use multiple linear regression or multiple quantile regression (for non-parametric data) to assess these variables independently on scores between the two groups. We will measure skills decay between groups using an analysis of variance (ANOVA) or a non-parametric analysis of variance at 0, 1 and 3-month assessments. Questionnaire results will be compared between groups using Chi-Square, independent t-test, or Wilcoxon rank sum where appropriate.

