The research settings for recruitment and enrollment of patients is Northwestern Memorial Hospital, Northwestern University, Chicago, IL. Patients will be recruited either at the medical center (while the patient is hospitalized) or during a clinic visit. The co-investigators, who provide care to patients with ventricular assist devices (VADs) will share information about the study with patients. If the patient's caregiver is not present at this time, we will contact them via phone or via mailed brochure to explain the study and then consent in person when they arrive for their VAD training.

The PI, CO-I or VAD nurse, will further explain the study to patients and caregivers, encourage them to ask questions, and obtain written informed consent. Patients and caregivers will be informed that if they decline to participate in the study, it will not prejudice current patient care, and they may discontinue participation at any time during the study with no adverse impact to their treatment or care. Verbal and written information provided to potential participants during informed consent will include the following: the purpose of the study, the nature of the questions asked during interviews, the method and frequency of skills assessment completion, the length of time required, the voluntary nature of participation in the study, the ability to not respond or participate in any parts if requested, the freedom to withdraw from the study at any time without consequences, the potential risks and benefits of study participation,

and the confidentiality of information gathered. A brochure with an overview of the study will also be provided. Patients will also be shown their study results, if desired. Patients who are enrolled in INTERMACS will also be informed that INTERMACS will securely transmit data to Northwestern, as well, which is already done for other studies. We will also incorporate language into their consent form that includes a statement about INTERMACS protected health information being transmitted securely to Northwestern. Patients who agree to participate in the study will sign an informed consent form. A copy of the signed consent form will be given to the patient, a second copy of the consent form will be placed in the patient's medical record, and the original copy will be kept and filed by the RC

NUMBER OF LOCAL PARTICIPANTS:

We expect to recruit 75 patients and 75 caregivers. One caregiver will be identified by each patient subject.

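### The primary checklist comparison counts both members of 75 patient-caregiver pairs as independent people, so its 5% level and stated power do not hold if scores within a pair are positively correlated.

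*Combined protocol and SAP*

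**What the plan says.** Under Data and Specimen Management, the sample size statement reads "Sample sizes of 65 in each group (total =130) achieve 82% power to detect at least 10% difference". It assumes means of 85% (SD 25) and 95% (SD 10) and a two-sided 0.05 t-test. Because non-normal scores are expected, it continues: "adding 15% requires 75 in each group". The primary comparison is then "We will compare checklist scores on actual patient assessments between usual care and SBML-trained groups using the independent t-test or Wilcoxon rank sum test".

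Under Number of Local Participants, recruitment is described differently: "We expect to recruit 75 patients and 75 caregivers. One caregiver will be identified by each patient subject". Procedures Involved confirms that this is the total over both arms: "up to 75 participating patients and 75 caregivers will be eligible to receive either the SBML VAD self-management curriculum or usual VAD training".

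The same section sets out how the two people are linked:

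- Enrolment is joint: "Patients and caregivers must both agree to participate in the study to be enrolled".
- Training is joint. In the usual arm, "the VAD nurse trains the patient and caregiver per usual routine with a non-implanted VAD"; in the SBML arm both practise together on the simulator.
- Both are then scored on the five skill domains on the actual VAD patient.

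On allocation it says only "Study randomization will be conducted via random number generator", with neither the unit nor the ratio. Hypothesis 1a, under Objectives, covers patients and caregivers together. The only provision for clustering is a random-effects model for repeat infections within a patient, in exploratory Aim 2.

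**The concern.** The analysis needs 75 independent observations per group, and the trial supplies 75 pairs in total. Two people who live with the same device, train together with the same nurses and demonstrate skills on the same patient are unlikely to give unrelated scores. An independent t-test or rank sum test treats them as unrelated. Positive correlation would make the estimated standard error too small, so the primary test would exceed its 5% level and any confidence interval would be too narrow, whatever the true effect. The 82% power figure rests on the same assumption of independence. The fallback linear or quantile regression has no pair term either, so adjustment would not cure the problem.

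**Working it through.** **Inputs from the plan.** SD 25 (usual) and 10 (SBML); difference 10 points; two-sided 0.05; 65 per group, raised by 15%; 75 pairs. **Assumed:** 1:1 allocation, both members of a pair in the same arm, and the ICC, for which the documents give no value.

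**1. The plan's own figure.** With 65 independent people per arm, SE = √((25² + 10²)/65) = √(725/65) = 3.34, and 10/3.34 = 2.99. The Welch degrees of freedom are 725²/(625² + 100²) × 64 = 84. The noncentral t gives 84.1% power. With a rank test at relative efficiency 3/π it is 82.4%, and a simulated Wilcoxon test gives 81.1%. So 82% is reproduced to within about 2 points, given independence. The inflation is 65 × 1.15 = 74.75, rounded to 75.

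**2. Counting units.** 75 per group × 2 = 150 observations. Recruitment is 75 + 75 = 150 people in 75 pairs, or 37.5 pairs per arm. The two agree only if both members of every pair are counted.

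**3. Error rate.** With two people per pair in one arm, the variance of an arm mean is multiplied by 1 + ICC. The planned SE is therefore too small by 1 − 1/√(1 + ICC), and the large-sample two-sided error rate is 2(1 − Φ(1.96/√(1 + ICC))). Simulation used 38 + 37 pairs, normal scores and 40,000 runs (Monte Carlo SE about 0.1 point).

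| ICC | SE too small by | Error rate, formula | t-test, SD 25 vs 10 | Wilcoxon, SD 25 in both arms |
|---|---|---|---|---|
| 0 | 0% | 5.0% | 5.0% | 4.9% |
| 0.1 | 5% | 6.2% | 6.0% | 6.2% |
| 0.2 | 9% | 7.4% | 7.2% | 7.1% |
| 0.3 | 12% | 8.6% | 8.2% | 8.3% |
| 0.5 | 18% | 11.0% | 10.8% | 10.6% |

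A t-test on pair means stays at 4.7% to 5.2% throughout.

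Two variations:

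- *Correlation in the usual arm only.* That arm carries 625/725 = 86% of the variance of the difference. At ICC 0.1, 0.2, 0.3 and 0.5 the t-test gives 5.8%, 6.8%, 8.1% and 10.3%.
- *Bounded, skewed scores* (mean 85, SD 25, 5-point steps; 20,000 runs). At realised within-pair correlations of 0.07, 0.14, 0.22 and 0.40, the t-test gives 5.8%, 6.6%, 7.6% and 10.0%, and the Wilcoxon test 6.2%, 6.8%, 8.0% and 10.0%.

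**4. Power of a test that holds 5%, for 10 points.** Effective n per arm is 75/(1 + ICC), or (75/1.15)/(1 + ICC) = 65.2/(1 + ICC) if the 15% is used up by non-normality. Power is from the noncentral t as in step 1.

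| ICC | Effective n, full 75 | Power | Effective n, after allowance | Power |
|---|---|---|---|---|
| 0 | 75.0 | 89.0% | 65.2 | 84.3% |
| 0.1 | 68.2 | 85.8% | 59.3 | 80.6% |
| 0.2 | 62.5 | 82.7% | 54.3 | 77.0% |
| 0.3 | 57.7 | 79.5% | 50.2 | 73.6% |
| 0.5 | 50.0 | 73.5% | 43.5 | 67.2% |

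Power falls to 82% at an ICC of about 0.20 to 0.22 with the full 75, and about 0.04 to 0.06 after the allowance. The lower value in each range is from pair means, the higher from effective n.

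**5. What the planned test would do at a true 10 points.** Ignoring pairs, it still rejects 88.0%, 87.0%, 86.3% and 84.3% of the time at ICC 0.1, 0.2, 0.3 and 0.5. Its fault is the error rate, not lost rejections.

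**6. The expected 33 points.** At ICC 0.5 after the allowance, SE = √(725/43.5) = 4.08 and 33/4.08 = 8.1. Power stays above 99%.

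**The case against.** *Pooling is inferred.* No sentence says patient and caregiver scores enter one test. If each role were analysed separately, the t-test would hold its level. This is a fair limit on certainty, but it does not rescue the plan: there would then be 37 or 38 people per arm, and power for 10 points would be about 60% (54% after the allowance), not 82%. The sample size paragraph is wrong on either reading, and pooling is the only one that reaches 75 per group.

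*The ICC is unknown and might be low.* SBML participants must all reach the passing standard (MPS), which may compress their scores, and a patient too ill to train is trained apart from the caregiver. This stands as a reason to show low values. At ICC 0.1 the error rate is only about 6%; the 11% figure needs 0.5, which nothing in the documents supports or excludes.

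*The written examination is also a primary measure.* In the usual arm only the caregiver is described as taking it. The figures here apply to the checklist comparison and should not be carried over.

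*The thresholds depend on a small slack.* The t-test with 65 per group gives 84.1%, not 82%, so the 0.04 to 0.06 threshold after the allowance reflects that gap of about 2 points. True; the power table is the better guide.

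*The conclusion would survive.* At 33 points it would. But a 5% level has to hold whatever the effect, and the plan sized itself on 10 points.

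**Conclusion.** The concern holds and should be fixed. As written, the checklist comparison treats 75 pairs as 150 independent people. With same-arm, 1:1 allocation of pairs, which the procedures imply but do not state, any positive within-pair correlation takes the test above 5%: to about 6% at an ICC of 0.1 and about 11% at 0.5. The stated 82% power for 10 points is secondary: a valid test reaches it only at low to moderate ICCs. The plan's statement that it is overpowered for a 33% difference stands. The direction of the error is certain for any positive ICC; its size depends on an ICC that the documents do not give.

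**What to change.** 1. State that the pair is the unit of randomisation and give the allocation ratio.
2. Replace the independent tests in the checklist comparison with a pair-aware analysis: pair means compared by t-test or Wilcoxon, or a mixed model or GEE clustered on the pair. Carry the pair term into the adjusted linear or quantile regression.
3. Restate the sample size as 75 pairs, about 37 or 38 per arm, with power for 10 points over an ICC range such as 0.05 to 0.5, with and without the 15% allowance. If the sponsor prefers a one-role primary analysis, say so and state the power of about 60% (54% after the allowance).

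One caution on the choice of test: with SD 25 vs 10 and equal means, the Wilcoxon test on pair means rejects 6.1% to 6.5% of the time. That comes from unequal spread, not pairing; the plain Wilcoxon test gives 6.2% there at ICC 0. With equal SDs the pair-mean version stays at 4.9% to 5.1%.

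The cost is protocol wording and one change of model, using data already to be collected. The stated power for 10 points becomes less favourable; power for 33 points is not materially affected.

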We will compare driveline infections and re-hospitalization rates at one and three months after VAD implantation between the SBML and the usual training groups using the Chi Square test, recognizing that we may be underpowered for this exploratory aim due to the short study time frame. We will compare age, sex, race/ethnicity, level of education, employment status, zip code, type of VAD, VAD indication (DT vs. BTT), and Charlson scores between groups using either the Chi Square test or independent t-tests. If there is a difference between the randomized groups in any of these variables at the level of $p \leq 0.1$, we will perform multiple logistic regression to control for these independent variables between groups. If some patients have more than infection, we will use random effects modeling to account for clustering by patient.

The study PIs, co-investigators, as needed, VAD nurse, and Research Coordinator (RC) will have access to individually identifiable data. Otherwise, a unique identification code will be assigned to each enrolled patient, and all of the data entered into the system for that patient will be identified by this code rather than by name.

Socio-demographic and medical records data will be collected by INTERMACS and exported to a secure web server at Northwestern University. Socio-demographic data collected from VAD caregivers and checklist of VAD self-maintenance tasks-performance data will be collected on paper but will be de-identified using a unique identifier for each patient or caregiver. This data will be stored on a Northwestern Server that is password protected and encrypted. All data will be collected specifically for research purposes.

WITHDRAWAL OF PARTICIPANTS:

Participants are free to withdraw from the study at anytime without consequences.

RISKS TO PARTICIPANTS:

There are two potential risks of participating in this study for patients:

1. Potential for breach of patient confidentiality. This is a very serious potential risk to patients, but safety measures, as described above, have been put into place and are monitored by the Northwestern University IRB.

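### Covariate adjustment hangs on p≤0.1 tests between randomised arms, with no stated order between the unadjusted and adjusted results; removing the screens and fixing one analysis in advance is a small, cheap improvement

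*Combined protocol and SAP*

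**What the plan says.** **Aim 1 (Data and Specimen Management).** The comparison is stated first: "We will compare checklist scores on actual patient assessments between usual care and SBML-trained groups using the independent t-test or Wilcoxon rank sum test". The sample size rests on the same kind of test, "with a significance level of 0.05 using a two-sided t-test". Eight variables are then tested between arms: age, sex, race/ethnicity, education, employment, zip code, type of VAD and VAD indication. The trigger follows: "If there is a difference between the randomized groups in any of these variables at the level of" p≤0.1. If it is met, linear or quantile regression is used "to assess these variables independently on scores between the two groups".

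**Aim 2 (same section).** Infections and re-hospitalisations are compared by chi-square. The same screen is run on nine variables (the eight plus Charlson score), and if it is met "we will perform multiple logistic regression to control for these independent variables between groups". The aim is called exploratory, "recognizing that we may be underpowered for this exploratory aim due to the short study time frame".

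**Elsewhere.** Procedures Involved says that allocation uses a random number generator. It also describes patient factors, Charlson codes among them, as assessed when an infection occurs and during re-hospitalisation. Data and Specimen Management names primary outcome measures (checklist and written examination scores). No section of the supplied text says whether the unadjusted or the adjusted result is primary.

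**The concern.** In a soundly randomised trial, a baseline difference between arms is a chance event. A test of that difference carries no information on whether the variable predicts the checklist score, which is the only reason to adjust for it. A strongly predictive variable that happens to be balanced stays out, and an irrelevant one that happens to be imbalanced goes in.

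The rule is also incomplete in two ways. It can mean that only the imbalanced variables enter the model, or that all listed variables enter once any one of them triggers. And it does not say whether the adjusted arm difference replaces, supports or merely accompanies the t-test or Wilcoxon result. Two analysts could both follow the text and headline different results.

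At stake are a modest amount of power, a little room for choosing between results and, for Aim 2, possible adjustment for something measured after randomisation.

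**Working it through.** **1. The plan's own power figure.** Inputs: means 85 and 95, SDs 25 and 10, 65 per group, two-sided 0.05. Root-mean-square SD = √((25² + 10²)/2) = √362.5 = 19.04. The noncentral t gives 84.4% (equal variance) or 84.1% (Welch), against 82% stated. Scaling n by the Wilcoxon efficiency 3/π gives 82.4 to 82.7%. The inflation reproduces: 65 × 1.15 = 74.75, so 75. The gap is small, conservative and a separate matter. What counts here is that the calculation contains no covariates, so it describes the unadjusted test.

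**2. How often the screen triggers by chance.** With k independent tests at 0.1 the probability is 1 − 0.9^k.
- Eight variables: 1 − 0.9⁸ = 0.570.
- Nine variables: 1 − 0.9⁹ = 0.613.
- If the tests are correlated 0.2 to 0.4: 54 to 48% (eight) and 58 to 51% (nine).

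**3. How often a given predictive variable is left out.** If only imbalanced variables enter: about 90%. If all enter once any triggers: 0.9⁸ = 43%.

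**4. Type I error, by simulation** (normal and bounded scores, 37 and 75 per arm).
- Adjusted result always replaces the unadjusted one: 3.6 to 5.1%. The low end occurs when the covariates explain 40% of the variance.
- More favourable of the two reported: about 5.3 to 6.6%.

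**5. Power for the 10-point target.** The correlation r between one covariate and the score is assumed; the documents give none. Both sizes are shown because 75 patients alone make 75/2 ≈ 37 per arm, while 75 patients plus 75 caregivers make 75 per arm if pairing is ignored. Bounded scores cannot exceed 100, which fits the plan's own expectation: "As the distribution of % items correct is likely to be non-parametric". The paired row assumes a within-pair correlation of 0.3, and its fixed set is three covariates plus role.

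Each cell gives unadjusted / rule, imbalanced only / rule, all listed / four fixed terms (%).

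| Setting | r = 0 | r = 0.3 | r = 0.5 |
|---|---|---|---|
| Normal, 37 per arm | 61/59/57/59 | 61/60/60/62 | 61/61/65/71 |
| Normal, 75 per arm | 89/89/88/88 | 89/89/90/91 | 89/90/93/95 |
| Bounded, 37 per arm | 62/59/54/60 | 62/60/55/62 | 63/62/60/68 |
| Bounded, 75 per arm | 93/92/90/93 | 93/93/92/94 | 94/93/94/96 |
| 37 pairs per arm | 80/80/80/80 | 81/81/81/83 | 83/83/86/89 |

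From the unrounded results, fixed set minus unadjusted:
- r = 0.3: from 62.4 − 61.9 = +0.5 (bounded, 37) to 91.1 − 89.3 = +1.8 (normal, 75).
- r = 0.5: from 96.1 − 93.6 = +2.5 (bounded, 75) to 70.9 − 61.0 = +9.9 (normal, 37).
- r = 0: from 79.5 − 80.0 = −0.5 (pairs) to 58.5 − 61.1 = −2.6 (normal, 37).
- Predictive variable outside the set (employment, r = 0.5, mixed variable types): 56.8 − 59.1 = −2.3 (37 per arm) and 87.7 − 89.0 = −1.3 (75 per arm).

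With a true 10-point effect, normal scores and 37 per arm, the unadjusted and all-listed results fall on opposite sides of 0.05 in roughly one trial in ten, and less often with 75 per arm.

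**6. At the anticipated effect.** With 61.47 (SD 24.48) against 94.88 (SD 6.63), bounded scores, 37 per arm and r = 0.3, power is 100% under every rule.

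**7. Aim 2.** If 5 to 30% of 75 patients have an event (assumed), there are 75 × 0.05 = 3.75 to 75 × 0.30 = 22.5 events. Over nine variables that is 3.75/9 = 0.42 to 22.5/9 = 2.5 events per variable, too few for a stable logistic model if all enter.

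**The case against.** The other side has a good case.
- The candidate variables, the threshold and the model families are all written down in advance. The t-test or Wilcoxon is named first and carries the sample size, so the regression reads as a follow-up. This stands as far as it goes: the unadjusted result is primary by implication. One sentence would make it explicit.
- Reporting the more favourable result is nowhere proposed, and under consistent use the rule does not inflate type I error. This stands. A reader might infer that the rule itself produces false positives; the figures do not support that.
- Leaving out a predictive variable in 90% of trials sounds like bias. It is not. Under randomisation the Aim 1 mean difference stays unbiased, and only precision is affected.
- The benefit of a fixed set depends on an r that the documents do not give, and it can be negative. Nothing in the documents favours age, education and VAD indication over the other listed variables. This stands, so the covariate set is a recommendation and not a requirement.
- The trial is described as having ample power at the expected effect ("Therefore, our study will be overpowered to detect a 33% difference"), and Aim 2 is exploratory. This limits the weight of the point.
- The Charlson timing is open to interpretation. The sentence in Procedures Involved can be read as scoring at the event, but Data and Specimen Management gives no time. The plan should exclude the event-time reading; it cannot be said to have adopted it.

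**Conclusion.** The point holds as a minor one. Both aims select adjustment variables on chance imbalance, the trigger is met in about half to 60% of correctly randomised trials, and no stated order links the two results that then exist.

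The firm conclusion is that the screens should go and one analysis should be fixed in advance. It rests only on random allocation and on the wording of the plan. The power figures rest on assumed values of r, an assumed within-pair correlation and simulated covariates. They show that the likely gain from a fixed set is slight at r = 0.3 and worthwhile only nearer r = 0.5.

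It would go too far to conclude that the Aim 1 result is at risk, that its error rate is materially inflated, or that a fixed covariate set is sure to help.

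**What to change.** **Both aims.** Delete the p≤0.1 screens. Tabulate baseline variables by arm without tests.

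**Aim 1.** Before outcomes are seen by arm, name one primary analysis, with the score and assessment time that it covers.
- Preferred: a regression with a short fixed set, entered whatever the balance, chosen by the team for expected prognostic value from the variables already listed. An example is age, education in three categories and VAD indication as known before randomisation (four model terms). Use robust standard errors, since the planned SDs differ (25 and 10). If patients and caregivers are pooled, add role and cluster by pair. Keep the unadjusted t-test or Wilcoxon as a sensitivity analysis that cannot replace the primary result.
- Acceptable: the unadjusted test as the sole primary analysis, stated as such. This is reasonable if the team expects none of the variables to predict the score.
- Raw zip code has too many levels to serve as a covariate. A pre-training score cannot serve either, because only the simulation arm takes that assessment.

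**Aim 2.** Name the unadjusted comparison as the main result. Do not enter all nine variables; one model adjusted for age alone could serve as a sensitivity analysis. Do not adjust for a Charlson score taken at infection or re-hospitalisation; use only comorbidities recorded before randomisation.

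**Cost.** Mostly analysis wording. Age and education are already collected; they are recorded after randomisation, but training cannot change them. VAD indication comes from INTERMACS, so its pre-randomisation value would have to be noted at enrolment, a small extra step. The statistical price is the power loss shown above if the chosen terms turn out not to be predictive.
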